## 10 Safety Analyses

Safety endpoints will be presented using descriptive statistics (Section 7.7). Safety analysis will be based on the Safety Set using actual treatment received.

### 10.1 Extent of Exposure

The number and percentage of subjects will be summarized by the number of doses received. The number and percentage of subjects assessed at each timepoint for CVAD will be also summarized by number of doses received.

### 10.2 Adverse Events

An AE will be classified as follow (See also Section 7.3):

- Pre-treatment AE: if it starts before the first study drug intake (AE onset date/time < date/time of first study drug intake);
- Treatment emergent AE (TEAE): if it starts on or after the first dose of study drug intake up to the end of the treatment period (date/time of first study drug intake ≤ AE onset date/time ≤ end date/time of the treatment period);
- Post-treatment AE: if the onset date is after the end of the treatment period (AE onset date/time > end date/time of the treatment period).

The treatment period is defined as the period between first study drug administration and the following end:

- For subjects who completed the treatment period without achieving treatment success, the end of the treatment period will be the date/time of the 180-minutes CVAD assessment;
- For subjects who achieving treatment success, the end of the treatment period will be the date/time of the CVAD assessment where patency is achieved;
- For subjects who discontinued the treatment due to AE or death, the end of the treatment period will be the start date/time of the relevant event and the event will be considered as treatment emergent;
- For subjects who discontinued the treatment due to other reasons, the end of the treatment period will be the date/time the last CVAD assessment performed.

An ADR is an AE related to study medication. A serious ADR is a SAE related to study medication.

A severe AE is an AE with severe intensity. Refer to Section 7.3 for missing severity.

An AE leading to discontinuation is an AE with action taken with study drug equal to “Drug Permanently Withdrawn”.

An AE leading to death is an AE with outcome equal to “Fatal”.

Two AEs with the same PT and classified in the same category (pre-treatment AE, TEAE or post-treatment AE) will be considered as two different events when calculating the “number of events” in the tables.

Pre-treatment AEs, TEAEs and post-treatment AEs will be presented separately. Pre-treatment AEs will be presented in the listings only.

A summary table displaying the number and the percentage of subjects experiencing at least one TEAE, serious TEAEs, ADRs/drug-related TEAE, serious ADRs, severe TEAEs, TEAEs leading to study drug discontinuation, TEAE of special interest (See Section 10.2.1) and TEAEs leading to death, as well as the number of events, will be presented by actual treatment group.

The SOC and PT will also be used for tabulation using the MedDRA dictionary. The number and percentage of subjects with at least one AE and the number of events will be presented by SOC and PT by actual treatment group for treatment emergent AEs, non-serious TEAEs, serious TEAEs, ADRs, serious ADRs, severe AEs, AEs leading to treatment discontinuation and AEs leading to death.

The number of subjects with the most common non-serious TEAEs (reported in  $\geq 5\%$  of subjects in any treatment arm) will be also displayed by SOC and PT. The number of events will be also included in this analysis. The number of subjects with TEAEs will be also displayed by SOC and PT and maximum severity.

Tables will be presented by SOC and then by PT, alphabetically sorted within each SOC and PT.

These tables will be repeated for the post-treatment emergent AEs.

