¹⁰ Collection of AEs and SAEs will begin from the time of Informed Consent signature. All AEs, TEAEs and SAEs on-going at the time the subject's study treatment ends should be evaluated up to 30 days after last administration of Study Drug. After this period, all unresolved TEAEs will be reported as "ongoing" in the CRF.

 Chiesi	Clinical Study Protocol
Clinical Study Code No.: CUSA-081-HEM-01	Version No.: 8.0
EUDRACT No./IND No.: 2019-002124-32/128551	Date: 21 FEB 2023

7.1.1 Visit 1

A screening visit will be conducted to identify eligible subjects to consent for the study. Screening will generally occur on the day of treatment (Day 1) but can also be performed on the day prior to treatment (Day 0) if needed for logistical reasons. Day 1 must be the following calendar day in this situation (for example Monday and Tuesday; not Friday and Monday).

Prior to any study assessments, examinations, or procedures being performed, the subject will sign the ICF.

It is imperative to confirm both eligibility and the subject's ability to undergo study drug instillations and assessments potentially lasting 3 to 4 hours. In the occasional circumstance where randomization needs to be rescheduled for the following calendar day, eligibility should be reconfirmed. The pharmacist or designee will access the IRT to obtain randomization allocation.

During the Screening Visit, the following procedures and assessments will occur:

- Written informed consent for each subject
- Review of the inclusion and exclusion criteria
- Collection of demographic data (birth date, sex, race/ethnicity)
- Medical history
- Weight and height
- Blood pressure measurement and heart rate
- A urine pregnancy test is requested for all females of childbearing potential. Women in physiological or surgical post-menopause do not need to be tested for pregnancy.
- AEs and concomitant medications/procedures to be assessed and recorded.
- CVAD history, including type, indication for insertion, and the number of hours the catheter has been known to be dysfunctional
- Determination of CVAD dysfunction, defined as the inability to withdraw 3 mL of blood ([section 7.2.3](#)), should be performed by a trained health care professional after the usual assessments, with repositioning and flushes, to confirm that an easily reversible or mechanical reason is not the suspected reason for poor catheter function.

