12.3.6 Safety Variables

Safety analysis will be based on SS set.

Adverse Events

All adverse events starting from the time the subject is administered the first dose of study drug on Day 1 until the withdrawal of study drug will be classified as treatment emergent adverse event (TEAE). The number of subjects who experience at least one TEAE, ADR, SAE, serious related TEAE, TEAE leading to study withdrawal, TEAE leading to death, and AESI (as defined in [Section 10.1](#)), will be summarized. Post-treatment adverse events during the 30-day follow up period will be summarized. Summaries will be presented by actual treatment arm and by system organ class and preferred term as the number and percentage of subjects having at least one event and the total number of events.

 Chiesi	Clinical Study Protocol
Clinical Study Code No.: CUSA-081-HEM-01	Version No.: 8.0
EUDRACT No./IND No.: 2019-002124-32/128551	Date: 21 FEB 2023

For AESIs, the percentage of subjects who experienced AESI and associated exact binomial 95% confidence interval will be provided in the summary.

All adverse events will be listed.

Vital signs

Vital signs (systolic and diastolic blood pressure, heart rate) will be summarized by means of descriptive statistics. Mean, min, max and standard deviation of the observed values will be presented, in addition to being listed.

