Listing 16.2.7.1	Pre-treatment Adverse Events (Intention-to-Treat Set)	AEL001	Add a new column 'AESI' after the Preferred term one and fulfil the name of the AESI category.	Footnotes: [1] System Organ Class and Preferred Term are coded using MedDRA Version 23.0. [2] "DTH" = results in death, "LTH" = is life-threatening, "HSP" = requires hospitalisation or prolongation of existing hospitalisation, "DI" = results in persistent or significant disability or incapacity, "CA" = is a congenital anomaly or birth defect, "SIG" = is a medically significant adverse event. [3] Onset Day is the study Day at Onset Date calculated with reference to the First Study Drug Administration Date.

Listing Number	Listing Title	Template Code	Notes	Footnotes
Listing 16.2.7.2	Treatment Emergent Adverse Events (Intention-to-Treat Set)	AEL002	Add a new column 'AESI' after the Preferred term one and fulfil the name of the AESI category.	Footnotes: [1] System Organ Class and Preferred Term are coded using MedDRA Version 23.0. [2] "DTH" = results in death, "LTH" = is life-threatening, "HSP" = requires hospitalisation or prolongation of existing hospitalisation, "DI" = results in persistent or significant disability or incapacity, "CA" = is a congenital anomaly or birth defect, "SIG" = is a medically significant adverse event. [3] [D1] is the study Day at Onset Date calculated with reference to the First Study Drug Administration Date. [D2] is the study Day at End Date calculated with reference to the First Study Drug Administration Date.
Listing 16.2.7.3	Serious Treatment Emergent Adverse Events (Intention-to-Treat Set)	AEL002	Same as Listing 16.2.7.2	Same as Listing 16.2.7.2
Listing 16.2.7.4	Non-Serious Treatment Emergent Adverse Events (Intention-to-Treat Set)	AEL002	Same as Listing 16.2.7.2	Same as Listing 16.2.7.2
Listing 16.2.7.5	Treatment Emergent Adverse Drug Reactions (Intention-to-Treat Set)	AEL002	Same as Listing 16.2.7.2	Same as Listing 16.2.7.2
Listing 16.2.7.6	Serious Treatment Emergent Adverse Drug Reactions (Intention-to-Treat Set)	AEL002	Same as Listing 16.2.7.2	Same as Listing 16.2.7.2
Listing 16.2.7.7	Severe Treatment Emergent Adverse Events (Intention-to-Treat Set)	AEL002	Same as Listing 16.2.7.2	Same as Listing 16.2.7.2
Listing 16.2.7.8	Treatment Emergent Adverse Events of Special Interest (Intention-to-Treat Set)	AEL002	- Same as Listing 16.2.7.2 - List only AESI events.	Same as Listing 16.2.7.2

Listing Number	Listing Title	Template Code	Notes	Footnotes

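### Treatment-emergent AEs are defined by onset time with no worsening criterion, so an AE that begins between consent and first dose and worsens after instillation can be missing from every safety table

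*SAP*

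**What the plan says.** AE recording starts before dosing. Protocol Section 7.1, schedule footnote 10, states: "Collection of AEs and SAEs will begin from the time of Informed Consent signature". Consent is given at screening, which is generally on the treatment day but "can also be performed on the day prior to treatment (Day 0) if needed for logistical reasons".

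SAP Section 10.2 then forms three classes from the onset date and time:

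- Pre-treatment: "Pre-treatment AE: if it starts before the first study drug intake".
- Treatment emergent: "if it starts on or after the first dose of study drug intake", up to the end of the treatment period.
- Post-treatment: onset after the end of the treatment period, with no upper limit stated.

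Of the first class it says: "Pre-treatment AEs will be presented in the listings only".

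Protocol Section 12.3.6 takes the same approach to treatment emergence, covering "All adverse events starting from the time the subject is administered the first dose of study drug on Day 1" until study drug is withdrawn. It limits the later summary: "Post-treatment adverse events during the 30-day follow up period will be summarized".

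SAP Section 10.2 also has a rule for subjects who stop treatment because of an AE or death. The treatment period ends when that event starts, and the event is deemed treatment emergent.

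**The concern.** A worsening clause is needed wherever AEs are collected before the first dose, because an event open at dosing can be aggravated by the drug. Schedule footnote 10 of the protocol has AEs that are ongoing when treatment ends evaluated for up to 30 days after the last administration, so such aggravation may well be observed. The SAP has no class in which to count it. The event keeps its pre-dose onset, goes to a listing, and drops out of the comparison between arms. For a thrombolytic instilled into a catheter, aggravation of something already present is a harm the safety tables should be able to show.

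This is more than missing detail. The rule as stated gives a definite classification, and for this kind of event the classification is wrong.

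**Working it through.** No figure in the plan bears on this point and no arithmetic is needed beyond counting tables. The check applies the SAP 10.2 rules to a test case.

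**Test case.** Let c be consent, o the AE onset, d the first intake, e the end of the treatment period and w the time of worsening. Take c < o < d < w, with o fully known and treatment not discontinued because of the AE.

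| Class (SAP 10.2) | Condition | Result |
|---|---|---|
| Pre-treatment | o < d | met |
| Treatment emergent | d ≤ o ≤ e | not met, since o < d |
| Post-treatment | o > e | not met, since o < d ≤ e |

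The time w enters none of the conditions. The result is the same whether the event becomes severe, serious or fatal.

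**Outputs.** SAP Section 16.1 has 18 AE tables (14.3.1.2.1 to 14.3.1.2.18) and 3 further tables (14.3.2.1 to 14.3.2.3), so 18 + 3 = 21. Each is titled as treatment emergent or as post-treatment. The test case is counted in 0 of 21. The text of SAP 10.2 mentions severe AEs and AEs leading to death without a qualifier, but the titles of the corresponding tables restrict them. The only pre-treatment output is Listing 16.2.7.1.

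**Provisions that might rescue the event.**

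1. *Discontinuation rule, SAP 10.2.* If the worsening stops treatment, the event is deemed treatment emergent. Read literally for a pre-dose onset, this sets e = o < d, so the treatment period ends before it begins, and the pre-treatment condition o < d still holds. The two rules conflict. Discontinuations may be rescued; other worsening is not.
2. *Incomplete dates, SAP 7.3.* The worst-case allocation puts treatment emergent first, but only when a missing or incomplete date or time prevents allocation. A known pre-dose onset is allocated directly.
3. *Site recording, protocol 10.8.* Clinically significant changes at the visits after Visit 1 are to be reported as AEs. Section 7.1.1 describes screening and treatment together under Visit 1, so worsening on the dosing day is not clearly covered. Neither document requires a new record with a new onset.
4. *Intensity, protocol 10.3.* Each AE is rated on a 3-point scale. Nothing shows that the time of a change in intensity is captured.

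**With a worsening clause.** If d ≤ w ≤ e, the event enters Tables 14.3.1.2.1 to 14.3.1.2.3 and any serious, severe, ADR, AESI or fatal table whose criterion it meets. If w > e, it enters the post-treatment tables. Both parts are needed because SAP 10.2 ends the treatment period at the assessment where patency is achieved, or at the 180-minute assessment for those completing without success. Much worsening could fall after that.

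**The case against.** The strongest reply is that the gap is narrow. Consent is on the dosing day or the day before, and eligibility is reassessed if the days differ. Protocol Section 4.3 excludes known or suspected catheter-related bloodstream infection, high bleeding risk and clinical instability. Affected events stay visible in Listing 16.2.7.1, a site may record the worsening as a separate AE, and eCRF instructions outside these documents may tell it to. No efficacy result changes. All of this stands and limits the size of the problem. It does not supply the missing criterion.

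A reader might infer more than the documents support:

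- **That all serious or fatal worsening is lost.** The discontinuation rule can bring in an event that stops treatment, although it conflicts with the pre-treatment definition.
- **That minor pre-dose oozing which becomes major bleeding is lost from the AESI tables.** Protocol Sections 10.1 and 10.9 start AESI collection and reporting at the first dose, and major bleeding has its own threshold. An event that first meets it after dosing first exists as an AESI then. Nothing requires it to inherit the earlier onset.
- **That a number of affected subjects can be given.** The documents contain no rate of AEs open at dosing and none for their worsening.
- **That the open-ended post-treatment class mixes systematic with unsolicited reports.** Protocol Sections 7.1.1 and 7.1.2 already rely on spontaneous reporting of SAEs and AESIs between Visit 1 and Day 30, so that contrast is weak. What remains is a minor mismatch with the 30-day limit in protocol Section 12.3.6.

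**Conclusion.** The point holds in a limited form. An AE with a known onset between consent and first dose that increases in intensity or becomes serious after instillation, without causing discontinuation, is classed as pre-treatment. It is counted in 0 of 21 AE and AESI tables, unless the site opens a new record. The onset-only wording originates in protocol Section 12.3.6 as well as in SAP Section 10.2.

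Few events are likely, and their number cannot be estimated from the documents. The conclusion assumes that sites keep a worsening event under its existing record, which the documents neither require nor forbid. This is a minor correction worth making because it is cheap and concerns safety counts.

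**What to change.** 1. In SAP Section 10.2, extend the TEAE definition to AEs with onset before first intake that increase in intensity or become serious on or after first intake and up to the end of the treatment period. Count worsening after that as post-treatment.
2. Identify these AEs in the blinded data review before lock. The eCRF was final in April 2022 and nothing shows that it captures a worsening time, so state explicitly that such an AE is allocated to treatment emergent when that time is not recorded. SAP Section 7.3 cannot be cited for this as it stands, because it deals with incomplete AE start and stop dates.
3. Reconcile the new wording with the rule that an AE leading to discontinuation is treatment emergent, so that a pre-dose onset no longer meets two conflicting rules.
4. List the departure from protocol Section 12.3.6 in SAP Section 12.
5. As a minor alignment, limit the post-treatment AE tables to the 30-day follow-up (up to the Day 30 + 2 contact) and list later SAEs separately.

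The cost is a few sentences in the SAP, a short blinded review of AEs with pre-dose onset, and slightly higher TEAE counts. No new data are needed. SAP Section 12 describes lock and unblinding as still to come; the change has to be made before then.

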Subjects will exit the treatment algorithm when treatment success is achieved at the specified time points, or after assessment of CVAD function 90 minutes following the second instillation of study drug (time point 180 min), whichever occurs first. Once a subject exits the treatment algorithm, assessments of CVAD function are completed for Day 1. In unsuccessful cases, further treatments for restoration of catheter functionality may be provided per the site's standard of care for CVAD. At 180 minutes, or in the case of Early Withdrawal, if treatment success is not achieved, any subsequently administered standard of care and related outcome will be documented.

Subjects will be monitored for AEs (including SAEs and AESIs) during the treatment period (Day 1) from the time the subject is administered the first dose of study drug until the withdrawal of study drug at V1, and for spontaneously reported SAEs and AESIs afterwards up until the Day 30 (± 2 days) follow up assessment.

Concomitant medications and procedures will also be collected as part of the SAE reporting requirements.

At the end of Visit 1, subjects will be discharged with instructions on how to record and report the status of their CVAD during the 30-day follow-up period, including:

- Date of first recurrent catheter re-occlusion (for those with treatment success at V1),
- Date and type of any additional treatment they received for catheter dysfunction, and
- Date of catheter removal or replacement.

7.1.2 Visit 2

The Day 30 (± 2 days) follow-up assessment will occur by phone or in person if the subject has a scheduled clinic visit. Spontaneously reported SAEs, AESIs, and related concomitant medications will be recorded and the status of the CVAD function will be determined by asking the subject to respond to the questions provided at the V1 discharge.

 Chiesi	Clinical Study Protocol
Clinical Study Code No.: CUSA-081-HEM-01	Version No.: 8.0
EUDRACT No./IND No.: 2019-002124-32/128551	Date: 21 FEB 2023

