## 5 Sample Size

For the primary assessment of the superiority of CUSA-081 vs. placebo, a sample size of 450 in the active arm (CUSA-081), and 50 in the control arm (placebo), will provide >99% power to detect a difference of  $\geq 35\%$  using a two-sided test at significance level of 0.05. The expected placebo response rate is approximately 20%.

For the assessment of the non-inferiority of CUSA-081 vs alteplase, a sample size of 450 in the active arm (CUSA-081), and 300 in the control arm (alteplase) will provide 87% power at the 2.5% significance level (that is by using one-sided 97.5% confidence intervals (CI)) with a non-inferiority margin of -10%, assuming an equal response rate of 75% in the control arm (alteplase), and the active (CUSA-081) arm. A sample size of 450 in the active arm (CUSA-081), and 300 in the control arm (alteplase) will also provide 92% power to detect a difference of 10% between the success rates using a two-sided test at significance level of 0.05.

A minimum of 841 subjects will be randomized in order to achieve a minimum of 800 subjects completing the study.

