Table 14.3.1.1	Study Drug Exposure (Safety Set)	EXT001	The following rows will be displayed: 
 
- Exposure
 
- 1 Dose Administered [n and % to be displayed]
 
- Timepoint Assessed 
 
- 30 Minutes [n and % to be displayed]
 
- 60 Minutes [n and % to be displayed]
 
- 90 Minutes [n and % to be displayed]
 
 
 
- 2 Doses Administered [n and % to be displayed]
 
- Timepoint Assessed 
 
- 120 Minutes [n and % to be displayed]
 
- 150 Minutes [n and % to be displayed]
 
- 180 Minutes [n and % to be displayed]
 
 
 
	Source: Listing 16.2.5.1
Table 14.3.1.2.1	Summary of Treatment Emergent Adverse Events (Safety Set)	AET001	Data to display: 
 
- Number of Subjects with at Least One TEAE
 
- Number of Subjects with at Least One Serious TEAE
 
- Number of Subjects with at Least One ADR
 
- Number of Subjects with at Least One Serious ADR
 
- Number of Subjects with at Least One Severe TEAE
 
- Number of Subjects with at Least One TEAE Leading to study Drug Discontinuation
 
- Number of Subjects with at Least One TEAE of Special Interest
 
- Number of Subjects with at Least One TEAE Leading to Death
 
	Source: Listing 16.2.7.2  Footnotes: [1] ADR = Adverse drug reaction; TEAE = Treatment emergent adverse event.
Table 14.3.1.2.2	Treatment Emergent Adverse Events by System Organ Class and Preferred Term (Safety Set)	AET003		Source: Listing 16.2.7.2  Footnotes: [1] System Organ Class and Preferred Term are coded using MedDRA Version xx.x

Table Number	Table Title	Template Code	Notes	Footnotes/Source Listing Number
Table 14.3.1.2.3	Treatment Emergent Adverse Events by System Organ Class, Preferred Term and Maximum Severity (Safety Set)	AET005	The number of events (“E”) columns will not be displayed.	Source: Listing 16.2.7.2  Footnotes: [1] System Organ Class and Preferred Term are coded using MedDRA Version xx.x [2] If a subject reports the same AE more than once within that SOC/PT, the AE with the maximum severity will be counted.

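### The treatment-emergent window closes at patency, so the TEAE percentages compare arms over observation times that depend on efficacy

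*SAP*

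**What the plan says.** **Window.** SAP 10.2 counts an event as treatment-emergent from the first dose to the end of the treatment period. For a cleared catheter it says: "For subjects who achieving treatment success, the end of the treatment period will be the date/time of the CVAD assessment where patency is achieved". For a subject who finishes without success, "the end of the treatment period will be the date/time of the 180-minutes CVAD assessment". Checks are at 30, 60 and 90 minutes and, after a second dose, at 120, 150 and 180. Two subjects who both follow the plan can therefore have windows of 30 and 180 minutes. Protocol 12.3.6 closes the window when study drug is withdrawn. Since success ends treatment, that gives the same dependence in practice.

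**Tables.** In SAP 16.1, the summary Table 14.3.1.2.1 opens with "Number of Subjects with at Least One TEAE". It and Tables 14.3.1.2.2 to 14.3.1.2.10 present subjects (and mostly events) by arm, without time at risk. Later events go to separate post-treatment Tables 14.3.1.2.11 to 14.3.1.2.18. Those cover SOC/PT, maximum severity, serious, non-serious, ADR, serious ADR, severe and common non-serious events. They include no overall summary, AESI or death table. The AESI tables (14.3.2.1, 14.3.2.2) and the death table (14.3.2.3) are treatment-emergent only.

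**Collection.** Protocol 7.1.1 monitors adverse events until study drug is withdrawn at Visit 1, "and for spontaneously reported SAEs and AESIs afterwards up until the Day 30" contact. Protocol 10.8 instead has all adverse events recorded from consent to the end of participation, including those found by open questions.

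**The concern.** Time to patency is the efficacy result, and here it also sets how long each subject is watched for a TEAE. An event at minute 60 is treatment-emergent in a subject who is still occluded, but post-treatment in one cleared at minute 30. If events occur at the same rate per minute in every arm, the arm that clears more catheters, or clears them sooner, will show a lower TEAE percentage with no true difference in safety. The reader of the main safety tables could not tell fewer events from less observation. If Protocol 7.1.1 governs collection, the effect goes beyond labelling: a non-serious event at minute 100 is sought in a failure but may never be recorded in an early success.

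**Working it through.** **Inputs from the documents**
- Placebo success by 90 minutes, SAP 5: "The expected placebo response rate is approximately 20" percent.
- Active success by 90 minutes, SAP 5: 75%, "assuming an equal response rate of 75% in the control arm (alteplase), and the active (CUSA-081) arm".
- Historical alteplase, SAP 5.1 Table 3: 516/995 at 30 minutes and 747/995 at 120 minutes, interpolated to 670/995 at 90.
- Historical reteplase, Protocol 1.3: 66.9% at 30 minutes, 88.5% at 60.

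**Reproducing the plan's figures.** The plan states no observation time by arm, so I checked figures that use the same rates.
- Non-inferiority power: 0.10 / sqrt(0.75×0.25/450 + 0.75×0.25/300) = 0.10/0.03227 = 3.098. Then Φ(3.098 − 1.960) = 87.3%, against the SAP's "will provide 87% power at the 2.5% significance level".
- Interpolation: 516 + (747 − 516)×60/90 = 670, as stated. The same line gives 593 at 60 minutes.

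**Formula.** Mean window = Σ (share first patent at a check × check time) + share never patent × 180, using nominal times.

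**Assumptions.** The documents give no time course for placebo, so its 20% is spread evenly over 30, 60 and 90 minutes. The active 75% follows either the historical alteplase shape (516/670 = 77.0% of 90-minute successes by 30 minutes, 593/670 = 88.5% by 60) or an even spread. Second doses either add nothing or work like first doses.

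**Worked case, alteplase shape, no second-dose gain**
- Active, cumulative 57.8%, 66.4%, 75%: 30×0.578 + 60×0.086 + 90×0.086 + 180×0.25 = 75.3 min.
- Placebo: (30 + 60 + 90)×0.0667 + 180×0.80 = 156.0 min.
- Ratio 75.3/156.0 = 0.48.

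| Active-arm assumption (placebo 20%) | Active, min | Placebo, min | Ratio |
|---|---|---|---|
| 75%, alteplase shape, no second-dose gain | 75.3 | 156.0 | 0.48 |
| 75%, alteplase shape, second dose like first | 65.9 | 151.2 | 0.44 |
| 75%, even spread, no second-dose gain | 90.0 | 156.0 | 0.58 |
| 75%, even spread, second dose like first | 84.4 | 151.2 | 0.56 |
| Historical alteplase, 67.3% by 90 min | 75.1–86.0 | 151.2–156.0 | 0.50–0.55 |
| Historical reteplase (several placebo splits) | 48–54 | 144–156 | 0.31–0.37 |
| 55% (smallest powered effect) | 91–114 | 151.2–156.0 | 0.60–0.73 |

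**Bounds at 75% and 20%, any time course, no second-dose gain.** Lowest: (0.75×30 + 0.25×180)/(0.20×90 + 0.80×180) = 67.5/162 = 0.42. Highest: (0.75×90 + 0.25×180)/(0.20×30 + 0.80×180) = 112.5/150 = 0.75.

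**Effect on a TEAE percentage (illustrative hazard).** Take one constant hazard in both arms that gives 5.0% on placebo under the SAP window. In the worked case the active arm then shows about 2.4%, or 2.1% if active second doses work like first doses. With a fixed 180-minute window both arms would show about 5.8%. In 53 placebo subjects, 5.0% is 2.7 subjects and 2.4% is 1.3.

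**CUSA-081 against alteplase.** At 75% in both arms with the same time course, the ratio is 1.0. If CUSA-081 reached 85% against 75% (alteplase shape), it would be 61.3/75.3 = 0.81 without second-dose gain and 55.0/65.9 = 0.83 with it.

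**The case against.** Much of the opposing case stands.

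- **Time at risk is nearly there.** SAP 10.1 and Table 14.3.1.1 give the numbers assessed at each check by arm. Apart from missed checks, and provided the one-dose rows include everyone given a first dose, 30 minutes × the sum of those counts approximates total window time. Only the division is missing.
- **No recorded event is lost from reporting.** Event counts can be added across the treatment-emergent and post-treatment tables, and the listings allow subject-level combination. But subject counts cannot be added, because one subject may appear in both sets, and the overall summary, AESI and death tables have no post-treatment counterpart.
- **Part of a lower rate may be real.** A shorter window is also a shorter drug dwell with fewer second doses. A constant hazard equal in all arms is my assumption; events clustered at instillation would change the size of the effect.
- **The window is the protocol's own, and the stakes are limited.** TEAEs are the named safety variable and safety is descriptive. In the placebo arm the illustrated shift is about one subject, and the exact 95% interval for 2/53 is 0.5% to 13.0%. The early stop recorded in SAP 12 may leave that arm smaller.

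A reader might go further and infer that CUSA-081 will look safer than alteplase because it acts faster. The documents do not support that as an expectation: Protocol 1.3 calls faster onset only possible, on limited data, and SAP 5 plans on equal success rates.

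**Conclusion.** The point holds as a presentation bias. Window length depends on the efficacy outcome, and no planned table gives either a rate per time at risk or a combined-window count of subjects. At 75% against 20% the mean active window is about 0.44 to 0.58 of the placebo window; over wider assumptions the range is about 0.3 to 0.75. Under an equal per-minute hazard, active-arm TEAE percentages fall roughly in the same proportion. The size rests on the assumed time courses and nominal check times.

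Two stronger readings are not supported. One is that active-arm subjects are known to be observed half as long: the documents fix no placebo time course, so about half is a central value. The other is that a common Day 30 window would by itself equalise all adverse events. If Protocol 7.1.1 governs, active collection of non-serious events stops at drug withdrawal, so their counts stay patency-dependent in any window. Efficacy analyses and type I error are unaffected.

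**What to change.** Keep the protocol-defined TEAE tables; making them supplementary is not needed.

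1. Beside them, print total window time per arm, consistent with Table 14.3.1.1, and events per 100 subject-hours.
2. In SAP 10.2 and 16.1, add combined tables from first instillation to the Day 30 contact for all treated subjects. Cover at least the overall summary, SAEs, AESIs, serious ADRs and deaths. SAEs and AESIs are collected in the same way for everyone after Visit 1.
3. Reconcile Protocol 7.1.1 with Protocol 10.8 on non-serious events after Visit 1. If 7.1.1 governs, add a footnote, including on the any-event row of the combined summary, that non-serious counts remain patency-dependent and should be read through the exposure-adjusted rates.
4. List the additions in SAP 12 before unblinding.

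The cost is SAP wording, a few columns and a small set of tables. The onset and assessment times are already required by SAP 10.2, so no new data are needed. The small downside is that Day 30 tables include background events unrelated to the instillation, which is a further reason to keep the TEAE tables alongside.
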